Direct Intervention Arm Cost. The main intervention costs are labor inputs, consisting of the one-time fixed labor cost of training and the variable labor cost of conducting the adherence intervention. To calculate training cost, we will multiply [name] and the ophthalmic technician's respective wage rates, including fringe benefits cost, by the 3 hours needed for training. Training cost will be applied in the base-case analysis, but because training cost attenuates over time as more patients are treated, it will be excluded in sensitivity analysis. For each one-on-one session and monthly booster phone calls with the patient/companion, the

interventionist will log the session and phone call times. These times will be multiplied by the technician's wage rate to estimate intervention variable labor cost. The non-labor cost inputs will consist of the smart bottles and eye drop aids provided to patients. The fixed training, variable intervention labor and non-labor inputs will be aggregated and then divided by the number of patients in the intervention arm to derive per-patient intervention cost.

Direct Control Arm Cost. Time of each one-on-one session with the patient/companion will be logged and multiplied by the technician's wage rate to estimate per-control patient cost.

Indirect cost. The VA healthcare system also incurs costs, such as administration, utilities, and custodial services that cannot be directly attributed to a given health care service but nonetheless should be included in the cost analysis. We will collect direct and indirect costs observed for ophthalmology clinic stop codes in the VA Decision Support System (DSS) extract for the Durham VA Medical Center. These will be used to calculate a direct-to-indirect cost multiplier. This multiplier will be applied to the estimated direct intervention and control arm costs to estimate their respective total costs. For both intervention and control arm costs, we will only account for costs that are likely to be incurred in "real world" clinical care; study-driven costs will be excluded. For example, the education session provided to control arm patients isn't likely to occur in usual clinical care and will not be included in the cost estimate.

Resource utilization. Expenditures are impacted not only by the cost of the intervention itself but also on other ophthalmology goods and services utilized. Therefore, we will collect glaucoma medication data from the VA Decision Support System Pharmacy extract. Using eye clinic stop codes and glaucoma diagnosis codes, we will collect outpatient costs incurred during the study period from DSS outpatient extracts.

Patient costs. Attendance of the one-on-one sessions will require the patients and/or companion to incur travel cost and may require that he/she miss work in order to attend the session. We will account for these indirect costs by asking the patients and companions to self-report how far they traveled round trip to attend the one-on-one session and whether they or their companion had to take time off from work to attend the session, and if so, how much time they took off. We will estimate travel cost by self-report and multiply the number of miles traveled by the deduction allowed by the Internal Revenue Service for medical-related travel. We will multiply time missed from work by an average hourly wage rate. The indirect costs reported in each arm will be aggregated and then divided by the respective group samples to estimate per-patient indirect cost.

Cost-Effectiveness. The 3 cost-effectiveness ratios that we will measure are: 1) cost per percentage improvement in medication adherence; 2) cost per blindness averted; and 3) cost per QALYs saved. We will consider the intervention to be cost-effective if the incremental cost-effectiveness ratio is \leq \$100,000 per QALY saved or \$150,000 per QALY saved, as recently recommended.⁶⁷ The estimation of these ratios are provided in the Data Analysis section below.

Data Analysis for Cost. The analysis will begin with standard descriptive statistics of the cost and effectiveness variables. We will then conduct bivariate analyses to assess statistical significance of group mean differences. If the main outcome is significantly different between the two groups, the first incremental cost-effectiveness ratio will be based on cost and improvement in medication adherence during the study period. However, incremental cost per blindness averted and QALYs saved will require simulating costs and outcomes among a larger hypothetical population and a time horizon beyond the study period. We will estimate

these ratios by replicating the Markov model developed by the Centre for Eye Research Australia.⁶⁸ We will use 2nd order Monte Carlo simulation to incorporate probabilistic sensitivity analysis into the base-case estimates and to estimate confidence intervals of the incremental cost-effectiveness ratios. We will also conduct extensive parameter and model sensitivity analyses to assess the robustness of the base-case results. If the main outcome is not statistically significant between the two groups, then the economic analysis will focus on differences in intervention costs and health care costs between the two groups during the study period.

Budget and Workflow Impact. For planning purposes it will be helpful for VA administrators to know what impacts implementing this adherence intervention will have on budget and workflow. We will use US glaucoma prevalence information available in the literature⁶⁹ to extrapolate the number of Veterans that are likely to be affected by glaucoma annually. We will multiply this target patient population by the intervention and health care resource utilization costs observed first by the treatment arm patients and then by the control arm patients. The difference between these 2 estimates will be the incremental budget impact of the intervention. Similarly, we will multiply this target patient population by the amount of per-patient time required to conduct the intervention in the treatment and control arms and the incremental time will be the workflow impact. We will convert the incremental workflow impact to full-time equivalents (FTEs).

1. Kingman S. Glaucoma is second leading cause of blindness globally. *Bulletin of the World Health Organization* 2004;82:887-8.

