The primary outcome for hypothesis 1A is the proportion of prescribed doses taken according to the electronic monitor. Participants in both arms will receive the electronic monitor or "smart bottle," which wirelessly transmits the date and time of opening of the smart bottle to the study team. From these medication events, the proportion of prescribed doses will be derived, defined as the ratio of the number of times the smart bottle was opened to the required number of doses prescribed according to the medical record over the period of time that the bottle is in use. For example, if a participant is advised to take his or her glaucoma drop twice a day for the 180 days that the bottle is in use and the smart bottle reveals 135 openings over the same time period, the proportion of prescribed doses taken is 37.5%.

Specific Aim 2. Evaluate the impact of the intervention on intensification of glaucoma therapy among Veterans at 12-months post randomization.

Hypothesis 2: The proportion of Veterans in the intervention arm that are prescribed more intensive glaucoma therapy, defined as addition of adjuvant glaucoma medication or recommendation for laser or glaucoma surgery will be less than the proportion of Veterans in the control arm who are prescribed more intensive glaucoma therapy in the 12 months following the intervention.

Baseline data collection will include cataloging the current glaucoma medication regimen prescribed to the participant. Chart abstractions will be performed at approximately 12 months following the randomization and intensification of glaucoma therapy will be defined as either 1) the addition of another glaucoma medication to the baseline regimen, 2) recommendation for glaucoma laser treatment, or 3) recommendation for glaucoma surgery in the 12 months following randomization. We will collect these data at approximately 12 months because the Metrics study suggested that 55% of participants in the control arm will have intensification of therapy within one year.

Specific Aim 3. Evaluate the incremental cost-effectiveness and budget and workflow impacts of the intervention compared to usual care.

Hypothesis 3: The intervention will be cost-effectiveness for the following ratios: 1) cost per percentage improvement in medication adherence; 2) cost per blindness averted; and 3) cost per quality-adjusted-life years saved.

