A direct measurement approach will be used to estimate per-patient intervention and control arm costs. Glaucoma-related health care utilization costs will be derived from VA administrative datasets. The cost estimates will be combined with observed improvement in medication adherence and reduction in escalation in therapy to estimate the first two incremental cost effectiveness ratios. Simulation using Markov modeling will be used to estimate the incremental cost per blindness averted and quality-adjusted life years (QALYs) gained. Cost estimates and labor time data collected will be combined with glaucoma prevalence rates among Veterans to estimate overall budget and workload impacts to the VA healthcare system.

Risk/Benefit Assessment

The intervention is educational in nature and does not impose physical risks to participants. The primary risks to participants are loss of time and confidentiality. Participants' time was considered as an important factor in designing an intervention which is efficient yet hopefully effective. Actions taken to mitigate the risk of loss of confidentiality are addressed in the sections "Privacy and Confidentiality" and "Information Security." If, in the course of the study, any information becomes available that might influence the course of clinical care of the participant, this information will be communicated directly to the treating provider. The study offers no definitive benefit to participants but the knowledge gained may lead to improvements in the management of glaucoma for future patients.

Selection of Subjects

We will screen individuals until we meet the desired sample size of randomizing 200 Veterans and enroll up to 200 of their companions (family or friend) if a companion is available. Enrollment of a companion will not be required for otherwise eligible Veterans to be included in the study.

Inclusion criteria for patients at datapull:

- 1) Diagnosis of open angle glaucoma [primary open angle glaucoma, pigment dispersion glaucoma, pseudoexfoliation glaucoma, combined mechanism glaucoma, low tension glaucoma] recorded in the medical record,
- 2) Prescribed glaucoma eye drops,
- 3) Visual field performed within the last 9 months. As visual field testing is standard care glaucoma and we wish to establish baseline glaucoma severity, we will require that subjects have a visual field test documented in the chart within 18months of enrollment.

Exclusion criteria for patients:

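### Observed health-care costs come only from pharmacy and outpatient extracts, so the cost of glaucoma surgery may be incompletely captured

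*Combined protocol and SAP*

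**What the plan says.** The rule is in Specific Aim 3, Resource utilization. It gives two sources. For drugs, "we will collect glaucoma medication data from the VA Decision Support System Pharmacy extract". For everything else, "Using eye clinic stop codes and glaucoma diagnosis codes, we will collect outpatient costs incurred during the study period from DSS outpatient extracts". No inpatient extract, operating-room record or procedure code is named there or elsewhere in the document.

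The stated scope is wider. The Aim 3 paragraph under Outcomes says "Glaucoma-related health care utilization costs will be derived from VA administrative datasets". Resource utilization opens by saying that spending depends on the intervention and "also on other ophthalmology goods and services utilized". The base case takes the VA's perspective.

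Surgery appears elsewhere in the plan. One component of intensification under Specific Aim 2 is "recommendation for glaucoma surgery in the 12 months following randomization". Table 1 and the list of 12-month data (Data and/or Specimen Acquisition) include surgery and laser in the chart abstraction. The Aim 3 paragraph under Outcomes also links cost to intensification: "The cost estimates will be combined with observed improvement in medication adherence and reduction in escalation in therapy".

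**The concern.** The plan sets out to count glaucoma-related care paid for by the VA and records who had surgery, but its cost query is not built to find every operation. A missing cost source cannot be repaired at the analysis stage, because the chart abstraction yields events and not costs.

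What is at stake is the direction as well as the completeness of the cost difference. If fewer intervention patients are operated on, the uncounted operations are savings, and the intervention looks more expensive than it is. If more are operated on, an added cost is hidden. The budget impact multiplies any per-patient error by the projected number of Veterans with glaucoma.

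**Working it through.** **Step 1. What the rule captures.** The text joins the two code lists with a single conjunction and does not say whether a record must match both or either. The site's coding of eye surgery is not given, so each possible route is set against each reading.

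| How the operation is recorded | Both codes required | Either code suffices |
|---|---|---|
| Outpatient, eye clinic stop code, glaucoma diagnosis | costed | costed |
| Outpatient, other stop code, glaucoma diagnosis | missed | costed |
| Inpatient stay | missed | missed |

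The pharmacy extract covers the added-medication part of intensification. It does not cost an operation.

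**Step 2. Which outputs use observed costs.**

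- *Primary outcome not significant* (Data Analysis for Cost): the analysis becomes a comparison of intervention and health-care costs between arms. Exposed directly.
- *Primary outcome significant* (same section): the adherence ratio uses cost during the study period. Exposed, because Outcomes places utilization costs among the cost estimates.
- *Budget and Workflow Impact*: observed utilization cost per arm is multiplied by the target population. Exposed directly.
- *Blindness and QALY ratios*: these come from a replicated Markov model. The plan does not say which trial costs enter it, so exposure cannot be determined.

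The first two are alternatives, so one of them is exposed whatever the trial result.

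**Step 3. Size.** The documents give no surgical cost, surgery rate or power figure for Aim 3, so there is no stated figure to reproduce. Let

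- m = share of surgical cost outside the extracts (assumed 0, 0.5 or 1),
- d = proportion operated on, control minus intervention (assumed 0.01 to 0.10),
- C = mean cost per operation (unknown, left as a symbol).

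Taking m and C as the same in both arms, the omitted cost difference per patient is D = m × d × C. With 200 Veterans randomized 1:1, there are 200 / 2 = 100 per arm, so the between-arm difference in uncosted operations is 100 × m × d.

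| m | d | D | Uncosted operations, difference |
|---|---|---|---|
| 0 | any | 0 | 0 |
| 0.5 | 0.01 | 0.005 C | 0.5 |
| 0.5 | 0.05 | 0.025 C | 2.5 |
| 0.5 | 0.10 | 0.05 C | 5 |
| 1 | 0.01 | 0.01 C | 1 |
| 1 | 0.05 | 0.05 C | 5 |
| 1 | 0.10 | 0.10 C | 10 |

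If d is positive, incremental cost is overstated by D. The adherence ratio then shifts by D divided by the adherence gain, and the budget impact by D times the target population. If d is negative, the signs reverse. If d = 0, then D = 0 and the comparison is unaffected, although each arm's total is still too low by m times its surgery rate times C.

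**The case against.** The best defence is that this is a gap in specification. Nothing shows under which stop code the site records eye surgery, or whether any of it is inpatient. If either code list suffices, outpatient surgery with a glaucoma diagnosis is caught. The general statement under Outcomes also points to a wider intent. This stands: only the inpatient omission follows from the text alone, and the outpatient omission is conditional.

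Early operations may also be few, since patients with intraocular surgery anticipated in the next 3 months are excluded and the cost horizon for the adherence ratio is 6 months. This stands in part. The educational session comes about 4 weeks or more after enrolment, so the exclusion covers at most about 3 − 1 = 2 of the 6 months after it.

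Four stronger readings are tempting, and the documents do not support them.

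- *All surgery is missed.* The site's coding and the and/or logic are not given.
- *Every ratio is affected.* Two of the three listed ratios ("1) cost per percentage improvement in medication adherence; 2) cost per blindness averted; and 3) cost per QALYs saved") come from the Markov model, whose cost inputs are not stated.
- *The trial predicts fewer operations and its economic case depends on them.* Hypothesis 2 is a composite that counts recommendations, not operations performed. The 55% control rate covers any intensification, with no surgical share. None of the listed ratios has intensification as its denominator, although Outcomes does link the two.
- *The omitted amount dwarfs the cost of the intervention.* Any dollar figure for surgery would be assumed, and the intervention cost includes training, booster calls, smart bottles and drop aids as well as session time.

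**Conclusion.** The concern holds as a limit on what the named cost sources can capture. As written, inpatient glaucoma surgery is not costed. Outpatient surgery under a stop code outside the eye clinic is not costed if both codes are required. This falls short of the plan's own scope for Aim 3.

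It bears on the between-arm cost comparison, the budget impact and the adherence ratio. It does not touch the primary outcome or Aim 2. The size cannot be fixed from the documents: under the assumed ranges it is 0 to 0.10 of the cost of one operation per patient, in the direction set by which arm has more surgery. The zero at equal surgery rates also relies on the missed share and the cost per operation being alike in the two arms. The change is worth making because the remedy is cheap and the omission cannot be undone by analysis.

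**What to change.** 1. State whether a record must match both code lists or either. Keep the stop-code rule for ordinary eye clinic visits.
2. Add DSS outpatient and inpatient records that carry a glaucoma laser or surgery procedure code, or a principal diagnosis of glaucoma, whatever the stop code. Count each record once.
3. Cut the data to each analysis's own window: 6 months after the intervention for the adherence ratio, and the study period for the cost comparison and budget impact. State how long the study period is. A single 12-month pull used for everything would not match the 6-month horizon.
4. Cross-check the costed procedures against the surgeries and lasers found at the 12-month chart abstraction, and report any without a matching cost record.
5. State whether observed procedure costs enter the Markov model.

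The cost is a somewhat wider query of the same administrative system and some plan wording, with no new patient contact. The downside is a noisier cost estimate, because operations are likely to be few and expensive. Confidence intervals for the cost difference will be wider, and a few patients may drive the result.

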[figure not shown]
The variables and data collection schedule are presented below (Table 1).

Baseline Data Collection: To reduce travel burden (and increase recruitment), we will strive to administer baseline surveys following informed consent on the day of a Veteran's scheduled appointment at the Durham VAMC or Hillandale clinic. However, we will make multiple dates and times available to the participants; and whenever possible, we will coordinate the baseline with a regularly scheduled appointment.

Randomization and Stratification: Participants will be randomized at the first informational session in a 1:1 allocation to the intervention or to the control arm. Randomization will be stratified according to if a companion is enrolled in the study with the participant. We anticipate 20% of participants will include a companion.⁶⁰ Randomization will also be stratified according to whether the glaucoma medication housed by the AdhereTech bottle is prescribed to be take once daily or more than once daily. Randomization status will be disclosed to the participant at the time of the intervention or control arm eye health education visit. Neither participants nor staff can be masked to randomization status.

Retention: To minimize participant burden and maximize their retention, screening is conducted over the phone. We will make multiple dates and times available to the participants; whenever possible, we will coordinate the baseline, education and information session and 6-month study visit with a regularly scheduled appointment. Our study staff will call participants prior to the intervention visit to confirm availability and remind them of the study appointment. In order to maximize retention during the follow-up phase of the study, study staff will contact participants by telephone as needed and ask about any problems using the smart bottle.

Study Flow:

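### Travel costing has no rule for trips shared with a regular appointment or for two people in one vehicle, so per-patient travel cost in the near-societal analysis can be overstated

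*Combined protocol and SAP*

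**What the plan says.** The Patient costs paragraph under Specific Aim 3 starts from the premise that "Attendance of the one-on-one sessions will require the patients and/or companion to incur travel cost". Distance is obtained by "asking the patients and companions to self-report how far they traveled round trip to attend the one-on-one session", and the analysts will "multiply the number of miles traveled by the deduction allowed by the Internal Revenue Service for medical-related travel". The arm totals are then formed: "The indirect costs reported in each arm will be aggregated and then divided by the respective group samples to estimate per-patient indirect cost".

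Four other places bear on this:

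- **Retention:** "whenever possible, we will coordinate the baseline, education and information session and 6-month study visit with a regularly scheduled appointment".
- **Randomization and Stratification:** "We anticipate 20% of participants will include a companion". The Educational Session paragraph has the companion attend with the Veteran.
- **Indirect cost (Specific Aim 3):** only costs likely in ordinary care are kept and "study-driven costs will be excluded". The control arm's education session is given as the example of a cost left out.
- **Opening of the Aim 3 analysis:** the base case takes the VA's perspective. Patient costs are collected in addition, to approximate a societal view.

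Table 1 marks Travel at baseline only, not at the education session. The baseline item in the Data and/or Specimen Acquisition section lists it as well, and the later-visit items do not.

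**The concern.** A cost belongs to the intervention only if the intervention caused it. A patient who was coming to the clinic that day anyway makes no additional trip for the session, and a companion in the same car adds no vehicle miles. The plan actively seeks the first situation and makes the second likely, yet it asks each person for a full round-trip distance and contains no step to separate additional miles from miles that would have been driven regardless.

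At stake is the travel component of the near-societal cost per patient and, depending on how control-session travel is treated, the incremental cost in that analysis. Vehicle sharing cannot be reconstructed later if nobody asks about it.

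**Working it through.** The plan states no travel-cost figure, so there is nothing to reproduce. The calculation below shows how far counted miles could exceed session-caused miles if the reported distances are used without adjustment.

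**Inputs**

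- Unit: one round trip, taken as equal for patient and companion (assumption).
- c = 0.20, the share of patients with a companion (Randomization and Stratification).
- s = share of trips that would have been made without the session. Not in the documents; assumed 0, 0.25, 0.50, 0.75.
- r = share of patient-companion pairs in one vehicle. Not in the documents; assumed 0, 0.5, 1.

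**Formulas, per patient**

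- Counted trips with no adjustment = 1 + c = 1.20.
- Session-caused vehicle trips = (1 - s) × (1 + c(1 - r)).
- Ratio = (1 + c) / [(1 - s)(1 + c(1 - r))].

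| s | r = 0 | r = 0.5 | r = 1 |
|---|---|---|---|
| 0 | 1.00 | 1.09 | 1.20 |
| 0.25 | 1.33 | 1.45 | 1.60 |
| 0.50 | 2.00 | 2.18 | 2.40 |
| 0.75 | 4.00 | 4.36 | 4.80 |

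The top row is the shared-vehicle effect alone, at most 1.20/1.00, or 20%. The r = 0 column is the same-day effect alone, 1/(1 - s).

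**Sensitivity to the companion assumption.** The table lets a separately travelling companion's trip be unnecessary on the same days as the patient's. If such companions came only for the session, session-caused trips are (1 - s) + c(1 - r). For s = 0.25, 0.50 and 0.75:

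- r = 0.5: 1.20/0.85 = 1.41, 1.20/0.60 = 2.00, 1.20/0.35 = 3.43.
- r = 0: 1.20/0.95 = 1.26, 1.20/0.70 = 1.71, 1.20/0.45 = 2.67.
- r = 1: unchanged from the table.

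**Effect on the increment**

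- If travel is counted alike in both arms, the expected difference is 1.20 - 1.20 = 0. The excess cancels, but so does the real extra travel of patients who came only for the intervention.
- If control-session travel is excluded, the excess stays in the increment. At r = 1 it is 1.20 - (1 - s), which is 0.20, 0.45, 0.70 and 0.95 of a round trip per patient for s = 0, 0.25, 0.50 and 0.75.

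**The case against.** The strongest reply is that this is an omission and not an instruction to overcount. Distance is asked in relation to attending the session, so a respondent already at the clinic could answer zero. The plan never says that the miles of two people in one car are added, and the wording of the Travel item is not shown. All of that is correct, and for that reason the conclusion is that travel cost can be overstated. Without an instruction, though, respondents will answer the same situation in different ways.

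Second, both arms attend one session under the same scheduling policy, randomization is stratified by companion, and the Patient costs paragraph forms totals in each arm. On that text the excess largely cancels. The exclusion of study-driven costs sits in a paragraph about the VA's indirect costs, and the plan does not say that it reaches patient travel. This stands: a reader might infer that the excess goes directly into the incremental cost, but that holds only if control-session travel is dropped, which the plan leaves open.

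Third, co-scheduling may be uncommon. It is sought only where possible, sessions are held at the Durham VA while some regular appointments may be at the Hillandale clinic, and timing is about 4 weeks or more after enrollment. This also stands, and it means that s could be small.

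Finally, patient costs lie outside the VA-perspective base case and outside the budget-impact calculation. That limits the reach of the point.

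**Conclusion.** The gap is real and cheap to close. If reported distances are used unadjusted, per-patient travel cost in the near-societal analysis can exceed what the session caused: by at most 20% from shared vehicles, given the planned 20% companion share, and by a factor of 1/(1-s) from trips that would have been made anyway (1.33 to 4.00 for assumed s of 0.25 to 0.75). That factor is exact for patients without a companion and somewhat lower overall if separately travelling companions came only for the session.

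A reader might infer that the plan prescribes double counting, or that the intervention's travel cost is overstated nearly fivefold. The documents support neither. They give no value for s or r, there is no excess if trips are made only for the session and in separate vehicles, and the 4.80 comes from the most extreme pair of assumptions. In absolute terms that case is 0.95 of one round trip per patient. No effect on a dollar figure or a cost-effectiveness ratio can be shown from the documents. This is a cheap improvement to a supplementary analysis.

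**What to change.** 1. When travel to the session is asked about, add two yes/no items for each person: whether they would have travelled there that day without the session, and whether patient and companion shared a vehicle.
2. In the societal-perspective analysis, count only session-caused miles, once per vehicle. Report costing of all trips as a sensitivity analysis.
3. Keep time off work as the extra time taken to attend the session. Do not set it to zero on shared days: a session of about 30 to 60 minutes added to a clinic visit can cost extra work time even when the trip is not extra.
4. State whether control-session travel is counted, so that the Patient costs and Indirect cost paragraphs give one answer.
5. Reconcile Table 1, which lists travel at baseline only, with the Patient costs paragraph, which costs travel to the session.

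The cost is two short questions, a few sentences in the economic analysis plan and one change to Table 1. The only downside is a slightly longer travel questionnaire.

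### The Aim 3 cost comparison is unadjusted although randomization is stratified, and the plan states neither the level at which intervention and patient costs enter it nor a clear interval method

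*Combined protocol and SAP*

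**What the plan says.** Under Data Analysis for Cost (Specific Aim 3), after descriptive statistics, the plan states: "We will then conduct bivariate analyses to assess statistical significance of group mean differences". No covariate, named test, interval method or treatment of skewed costs follows.

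Two cost components are described as averages. Under Direct Intervention Arm Cost, the training, labor and non-labor "inputs will be aggregated and then divided by the number of patients in the intervention arm to derive per-patient intervention cost". Under Patient costs: "The indirect costs reported in each arm will be aggregated and then divided by the respective group samples to estimate per-patient indirect cost". The raw inputs are individual: the "interventionist will log the session and phone call times", and patient costs come from "asking the patients and companions to self-report how far they traveled round trip to attend the one-on-one session", together with time taken off work. Medication and outpatient costs come from the VA Decision Support System (DSS) extracts and are not described as averaged. The control session "isn't likely to occur in usual clinical care and will not be included in the cost estimate".

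Under Randomization and Stratification there are two factors: "Randomization will be stratified according to if a companion is enrolled in the study with the participant", and "Randomization will also be stratified according to whether the glaucoma medication housed by the AdhereTech bottle is prescribed" once daily or more often. The Aim 1 model contains both (FREQ and COM) and cites regulatory guidance for doing so. The Aim 2 text has a health-literacy term mixed in with dosing frequency, but it states that the stratification variables are in the model.

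Data Analysis for Cost goes on to plan second-order Monte Carlo simulation with confidence intervals for the cost-effectiveness ratios. It also says that if the main outcome does not differ significantly, the economic analysis turns to differences in intervention and health-care costs over the study period.

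**The concern.** When randomization is stratified, the arms are balanced on the strata by design. An analysis that leaves the strata out still charges their variance to error, so its standard error is larger than the design warrants. The plan follows this reasoning in Aims 1 and 2 and departs from it in Aim 3 without giving a reason.

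The second part is a gap. A reader cannot tell whether session labor, aids, travel and lost work time enter the comparison as one value per participant or only as an arm mean. Nor can the reader tell how an interval for the within-trial cost difference, or for cost per percentage improvement in adherence, would be obtained.

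Both matter most when the primary outcome is not significant. The cost difference is then the main economic result, and a needlessly conservative test makes it easier to report no cost difference when there is one.

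**Working it through.** The documents give no cost mean, SD, power or alpha for Aim 3, so there is no planned figure to reproduce. What follows illustrates the effect of omitting the strata.

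**Inputs from the documents:** 200 randomized, 1:1 allocation, 20% expected to have a companion.

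**Assumptions:** two-sided alpha of 0.05; the strata explain a share R² of cost variance, with R² = 0.05, 0.10 and 0.30; in the simulation, half the participants are dosed more than once daily.

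**1. Interval width.** Unadjusted width / adjusted width = 1/√(1 − R²).
- R² = 0.05: 1/0.975 = 1.026, so 2.6% wider
- R² = 0.10: 1/0.949 = 1.054, so 5.4% wider
- R² = 0.30: 1/0.837 = 1.195, so 19.5% wider

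**2. Power where the adjusted test has 80%.** Power = Φ[(1.960 + 0.842)·√(1 − R²) − 1.960].
- R² = 0.05: 78.0%
- R² = 0.10: 75.7%
- R² = 0.30: 65.0%

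This formula lets the unadjusted difference vary as much as its standard error claims. If the arms are exactly balanced within strata, the difference varies less, and power is Φ[2.802 − 1.960/√(1 − R²)] = 78.5%, 76.9% and 67.7%. The first set is therefore the larger estimate of the loss; the conclusion is the same.

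**3. Type I error.** This was simulated with 4,000 runs per scenario, exact 1:1 allocation within strata and a nominal 5% level.
- R² = 0: unadjusted 5.4%, adjusted 5.4%
- R² = 0.10: unadjusted 3.8%, adjusted 5.2%
- R² = 0.30: unadjusted 2.0%, adjusted 5.5%

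The closed form 2·[1 − Φ(1.960/√(1 − R²))] gives 3.9% and 1.9% for R² = 0.10 and 0.30, in agreement with the simulation.

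**4. Level of the cost data.** Setting the sections side by side, times are logged by session and call, and travel and time off are self-reported by each patient and companion. The only derivation written down is total divided by number of patients. No sentence links either form to the bivariate test. The Monte Carlo intervals follow the text on the Markov model for blindness averted and QALYs, and do not clearly extend to the within-trial cost difference or to cost per percentage improvement in adherence.

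**The case against.** The strongest defense of the plan is that omitting the strata is safe: it never raises the false-positive rate, and if dosing frequency and companion barely predict cost, nothing is lost. The documents do not say that either factor drives cost. Companion status would act mainly through patient costs, which lie outside the VA-perspective base case. Aim 3 is the third aim, and the ratios have probabilistic sensitivity analysis. All of this stands and limits the size of the point. It does not explain why Aim 3 departs from the plan's own practice when adjustment costs nothing.

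A reader might go further and infer that dividing arm totals by arm size gives every participant the same cost, so that intervention and patient costs carry no sampling error and the intervals are too narrow. The documents do not support that. A total divided by n is the ordinary arm mean, the inputs are collected individually, and nothing says that the means replace participant values in the test. For the fixed training cost, a constant is correct. For session labor, the control side is excluded by design, so there is largely no control-arm counterpart to test. It would also be too broad to say that no ratio has an interval, given the planned simulation. The supportable statement is that the plan leaves the level of analysis open.

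**Conclusion.** The point holds in two parts. First, the cost comparison is unadjusted and ignores both randomization strata, contrary to the plan's approach in Aims 1 and 2. The effect is lost precision and a conservative test, not bias or false positives. For an assumed strata R² of 0.05 to 0.30, the interval is about 3% to 20% wider and power is about 78% to 65% against 80%, with a slightly smaller power loss under exact balance within strata. If R² is near zero, the loss is negligible.

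Second, the plan does not say at which level intervention and patient costs enter the test and gives no clear interval method for the within-trial cost difference. This is a gap in specification, not a demonstrated error, and no dollar figure can be put on it from the documents. It deserves closing because the cost difference becomes the focus of the economic analysis if the primary outcome is not significant.

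**What to change.** - Define a cost for each participant: logged session and call minutes times wage, aids received, own travel and time off for the patient-cost view, and own DSS costs. Add the per-patient share of the fixed training cost as a constant in the intervention arm.
- Replace the bivariate test by a regression of cost on arm, FREQ and COM, with bootstrap intervals to allow for skew and unequal variances.
- For cost per percentage improvement in adherence, resample each participant's cost and adherence together.
- State which intervals the Monte Carlo simulation supplies and which come from the bootstrap.

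The cost is mainly plan wording. Two data points need confirming: that aids are recorded per participant, since the plan says only that they are provided, and that travel to the education session is captured, since Table 1 lists travel at baseline only.

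Optionally, add each participant's eye-care and glaucoma-drug cost in the year before randomization as a covariate. This needs an earlier start date on the same DSS extracts. The interval is multiplied by √(1 − r²), which is 0.954, 0.866 and 0.714 for r = 0.3, 0.5 and 0.7, or 5%, 13% and 29% narrower. The documents give no value for r, so this is an efficiency option and not a correction.
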